6.1 Subject demographics/other baseline characteristics

Patient demographic and baseline characteristic data will be collected on all subjects.

6.1.1 Pregnancy assessments

All pre-menopausal women who are not surgically sterile will have a urine or serum pregnancy test performed at the Day 0 visit. Pregnancy testing is not required for post-menopausal women.

7 Study discontinuation and completion

7.1 Discontinuation

7.1.1 Discontinuation of study medication/supplement

Discontinuation of study medication/supplement for a subject occurs when the study medication/supplement is stopped earlier than the protocol planned duration, and can be initiated by either the subject or the investigator.

The investigator must discontinue study medication/supplement for a given subject if, he/she believes that continuation would negatively impact the subject's well-being. After study medication/supplement discontinuation, the patient should remain in the study, unless he/she withdraws consent, preferably in writing.

Study medication/supplement must be discontinued under the following circumstances:

- Subject decision
- Pregnancy
- Any situation in which study participation might result in a safety risk to the subject
- Any laboratory abnormalities that in the judgment of the investigator prevents the subject from continuing study medication/supplement administration

If discontinuation of study medication/supplement occurs, the investigator should make a reasonable effort to understand the primary reason for the subject's premature discontinuation of study medication/supplement and record this information.

Subjects who discontinue study medication/supplement or who decide they do not wish to participate in the study further should NOT be considered withdrawn from the study UNLESS they withdraw their consent. If discontinuation occurs after Day 14, study personnel should attempt to obtain Day 28 labs as close as possible to last dose of study medication/supplement taken.

Where possible, they should return for the Day 28 assessments indicated in the assessment schedule. If they fail to return for these assessments for unknown reasons, every effort (e.g. telephone, e-mail, and letter) should be made to contact the subject/pre-designated contact per institutional guidelines to collect as much data as possible according to the visit schedule.

Patient's vital status can also be verified by the study site upon contact with patient's primary care physician or other sources according to local rules and regulations.

After study medication/supplement discontinuation, at a minimum, in the abbreviated visit, the following data should be collected either during an in person visit or via telephone/email contact:

- new / concomitant treatments
- adverse events/Serious Adverse Events

7.1.1.1 Replacement policy

Subjects will not be replaced on study.

7.1.2 Withdrawal of informed consent

Subjects may voluntarily withdraw consent to participate in the study for any reason at any time. Withdrawal of consent occurs only when a subject:

- Does not want to participate in the study anymore
- And
- Does not allow further collection of personal data

It is encouraged that patient provides withdrawal of consent in writing.

In this situation, the investigator should make a reasonable effort (e.g. telephone, e-mail, letter) to understand the primary reason for the subject's decision to withdraw his/her consent and record this information. Patient's vital status can be verified upon contact with patient's primary care physician or other sources according to local rules and regulations.

Study medication/supplement must be discontinued and no further assessments conducted, and the data that would have been collected at subsequent visits will be considered missing.

Further attempts to contact the subject are not allowed unless safety findings require communicating or follow-up.

The study will continue to keep and use collected study information (including any data resulting from the analysis of a subject's samples until the time of withdrawal) according to applicable regulations.

7.1.3 Lost to follow-up

For subjects whose status is unclear because they fail to appear for study visits without stating an intention to discontinue or withdraw, the investigator must continue to attempt to contact the subject until the end of the study per institutional guidelines. A subject should not be considered as lost to follow-up until the end of the study. Vital status can be determined using publically available information in accordance with institutional guidelines.

7.1.4 Early study termination by the sponsor

The study can be terminated by the sponsor at any time. Reasons for early termination:

- Unexpected, significant, or unacceptable safety risk to subjects enrolled in the study
- Decision based on recommendations from applicable board(s) after review of safety and efficacy data

In making the decision to terminate, the sponsor will always consider the subject welfare and safety. Should early termination be necessary, subjects must be seen as soon as possible and treated as a prematurely withdrawn subject. The investigator may be informed of additional procedures to be followed in order to ensure that adequate consideration is given to the protection of the subject's interests. The sponsor will be responsible for informing IRB of the early termination of the trial.

7.2 Study completion

Study completion is defined as when the last subject finishes their Day 28 visit, and any repeat assessments associated with this visit have been documented and followed-up appropriately by the Investigator, or in the event of an early study termination decision, the date of that decision.

8 Safety monitoring and reporting

8.1 Definition of adverse events and reporting requirements

8.1.1 Adverse events

An adverse event is an untoward event that affects the patient's health or safety. When reporting an adverse event, the investigator will complete the AE report form. Adverse events that require reporting include any clinical changes in condition that could possibly be attributed to:

- Any of the study medication/supplements
- Any study required procedures (lab draws)

Each adverse event will be evaluated by the investigator for relatedness and seriousness.

i) Relatedness

The relatedness of an adverse event to the study medication/supplement will be assessed by the Investigator for each submitted adverse event form.

- **Possibly Related:** An adverse event that is noted in the package insert.
- **Unknown:** An adverse event that cannot be determined to have a causal relationship with either the study medication/supplement or study procedure will be classified as unknown.
- **Not Related:** An adverse event that is determined to not have a causal relationship with either the study medication/supplement or study procedure.

ii) Seriousness

Adverse events as described above will be evaluated for serious injury. Adverse events resulting in death or serious injury are to be reported to the sponsor within 24 hours of learning of the event. An adverse event (AE) or suspected adverse reaction is considered "serious" if, in the view of either the investigator or sponsor, it results in any of the following outcomes: death, a

life-threatening adverse event, inpatient hospitalization or prolongation of existing hospitalization, a persistent or significant incapacity or substantial disruption of the ability to conduct normal life functions, or a congenital anomaly/birth defect. Important medical events that may not result in death, be life-threatening, or require hospitalization may be considered serious when, based upon appropriate medical judgment, they may jeopardize the participant and may require medical or surgical intervention to prevent one of the outcomes listed in this definition.

iii) SUSARS

All Suspected Unexpected Serious Adverse Reactions (SUSARS) related to Rosuvastatin or supplements (if required per regulatory guidelines) are to be reported to the sponsor within 24 hours of learning of the event.

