10.6.1 Adverse events

All information obtained on adverse events will be summarized by study group. A subject with multiple adverse events of the same type is only counted once towards the total of that event. Serious adverse event and deaths resulting from an adverse events will be tabulated. All adverse events, deaths and serious adverse events will be provided in patient listings.

11 Ethical considerations and administrative procedures

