## **9. Analysis of Safety Data**

### **9.1. Adverse Events**

Adverse events will be summarized by study group. A subject with multiple adverse events of the same type is only counted once towards the total of that event, however the total number of adverse events experiences will also be calculated. Adverse events will be collected through the end of the study period. No formal statistical tests will be conducted. All summaries and analyses of the safety data will be conducted on the SAS.

Adverse events will be summarized in patient listings with the following characteristics:

- Seriousness (mild, moderate, severe potentially life threatening)
- Relatedness (possibly, unknown, not related)
- Status (expected, unexpected)
- Action taken (drug withdrawn, drug interrupted, not applicable, unknown)
- Resolution (unresolved, resolved, resolved with sequelae, unknown)
- Considered a serious adverse event

Adverse events occurring at least 5% of the time in the overall population will be summarized in a separate table.

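### The only general reporting criterion in Protocol 8.1.1 lets adverse events be screened by suspected cause before they are recorded, at odds with the rest of the plan

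*Protocol*

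**What the plan says.** Protocol 8.1.1 opens with a definition that has no causal condition: "An adverse event is an untoward event that affects the patient's health or safety". Its statement of what must be reported does have one: "Adverse events that require reporting include any clinical changes in condition that could possibly be attributed to" any study medication or supplement, or a required procedure such as a blood draw. No other general criterion is given for which non-serious events go on a form.

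Relatedness comes later. It "will be assessed by the Investigator for each submitted adverse event form", with three grades: possibly related, unknown and not related. The last is defined as "An adverse event that is determined to not have a causal relationship with either the study medication/supplement or study procedure". The SAP 9.1 listings carry the same three grades.

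For the tables, Protocol 10.6.1 says: "All information obtained on adverse events will be summarized by study group". SAP 9.1 also summarises events by group. It adds a separate table for events reaching 5% in the overall population, and it plans no formal tests.

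**The concern.** Causality is in effect judged twice, and the first judgement leaves no record. An event that staff think unrelated from the outset need not be submitted, so it never reaches the relatedness grade or the by-arm tables, which can hold only what was obtained. The periodic Medical Monitor reports in SAP 10 include the same adverse event tables and listings.

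At stake is the completeness of the safety data. Protocol 1.1 gives public belief that supplements are safer than statins as part of the trial's background, so readers will look at adverse events by arm. If the screen also worked differently from arm to arm, the tables could show a difference that is not real.

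**Working it through.** The plan states no figure on this point, so there is none to reproduce. The check sets the passages side by side and then illustrates the effect of a screen.

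**1. Passages compared**

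- Protocol 8.1.1, definition: no causal condition.
- Protocol 8.1.1, reporting criterion: possible attribution to a study product or procedure.
- Protocol 8.1.1, *possibly related*: "An adverse event that is noted in the package insert". This is a different test from the reporting criterion.
- Protocol 8.1.1, *not related*: applied to forms already submitted. An event can pass the reporting criterion and still be graded *not related* later, so the category can be used. It omits events dismissed at the start.
- Protocol 8.1.1, seriousness: "Adverse events resulting in death or serious injury are to be reported to the sponsor within 24 hours of learning of the event". The preceding sentence refers back to adverse events as already described, so it is unclear whether the attribution condition carries over.
- Protocol Table 7-1 (Day 28), Protocol 7.1.1 (contact after stopping study product) and SAP 9.1 (collection to the end of the study period): adverse events requested with no attribution limit.
- Protocol 8.1.2 (serious events in pregnancy) and SAP 9.3 (all-cause mortality): no attribution limit.

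No sentence says that only attributable events are reported, and none says that all are reported regardless of cause. Staff could follow either reading.

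**2. Undercounting, same screen in every arm**

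Let f be the share of true events that pass the screen. The documents do not give f, so a range is shown. The 5% cut-off is taken as 0.05 × 200 = 10 subjects, assuming that all 200 are in the safety set.

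- True rate needed for an expected recorded rate of 5%: 0.05 / f.
- Chance that an event with a true rate of 6% is recorded in at least 10 subjects: P(X ≥ 10), with X ~ Binomial(200, 0.06f).

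| f | True rate needed | P(X ≥ 10), true rate 6% |
|---|---|---|
| 1.0 | 5.0% | 0.77 |
| 0.9 | 5.6% | 0.64 |
| 0.75 | 6.7% | 0.41 |
| 0.5 | 10.0% | 0.08 |

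An equal screen leaves ratios between arms unchanged but shrinks differences. A true 30% against 10% gives a recorded difference of 0.20 × f: 20, 15 and 10 percentage points at f = 1, 0.75 and 0.5.

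**3. Screen that differs by arm (assumed)**

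With a true rate of 20% in both arms, the recorded rates are 0.20 × f in each arm:

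- f = 0.75 and 0.75: 15% and 15%, ratio 1.0.
- f = 0.9 and 0.5: 18% and 10%, ratio 1.8.
- f = 1.0 and 0.5: 20% and 10%, ratio 2.0.

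With 25 subjects per arm, 18% and 10% are 4.5 and 2.5 expected subjects.

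**4. Could the screen differ by arm?**

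Protocol 4.3.1 describes the placebo as comparable to rosuvastatin only, while the supplements are soft gels, capsules or a tablet. SAP Appendix A gives 28-day counts of 28 (rosuvastatin, placebo, Garlique), 56 (fish oil, cinnamon, red yeast rice), 84 (turmeric) and 112 (plant sterol). Count alone separates five of the six supplements from rosuvastatin but identifies only turmeric and plant sterol uniquely. Under Table 7-1, pill count and adverse event collection fall at the same Day 28 visit.

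**The case against.** The strongest reply is that the criterion is not restrictive. It says that reportable events include attributable changes, which does not exclude others. The definition is unconditional, several other sections ask for adverse events without limit, and a three-grade relatedness scale suggests that broad collection was intended. This stands against a reading that a reader might reach, namely that only attributable events are reported and that *not related* cannot be filled. The documents do not say the first, and the second treats different tests as one.

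A second reply is that nothing shows bias between arms. Investigator staff and assessors are to be blinded (Protocol 4.4). The criterion asks about attribution to any study product, so it can be applied without guessing the arm. The belief described in Protocol 1.1 is that of consumers, not of staff. Rosuvastatin and placebo share a pill count and are described in the SAP as visually similar. All of this stands. It would be tempting to infer that pill counts reveal the arms and that the safety tables will therefore favour supplements, but the documents support only the possibility.

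Neither reply supplies the missing statement that events are recorded regardless of cause. If that is the intention, the one general criterion in 8.1.1 does not express it.

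**Conclusion.** The reporting criterion in Protocol 8.1.1 is ambiguous and inconsistent with its own definition, with the planned *not related* grade, and with the unconditional requests for adverse events elsewhere in the protocol and SAP. Followed literally, it may give undercounted by-arm safety tables and an incomplete *not related* category, and this cannot be repaired after data collection.

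The size cannot be derived from the documents, and every reporting fraction above is an assumption. With fractions from 1.0 down to 0.5, the chance that a 6% event reaches the SAP's frequency table runs from 0.77 to 0.08. A false difference between arms arises only if the fraction differs by arm, which differences in product form and pill count make possible but do not demonstrate.

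The consequences are limited: adverse event comparisons are descriptive and the primary LDL-C analysis is unaffected. This is a cheap improvement to safety data quality, not a flaw in the trial's main inference.

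**What to change.** Replace the reporting criterion in Protocol 8.1.1 with a statement that every adverse event is recorded regardless of suspected cause, with relatedness graded afterwards. Start the period at the first study-required procedure and run it through the end of the study period, as in SAP 9.1. A start at first dose would drop events from the Day 0 blood draw, which the present text covers. Because the seriousness paragraph refers back to this text, the change would also settle the doubt about serious events.

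Keep the by-arm tables on all recorded events, as Protocol 10.6.1 and SAP 9.1 already plan. No SAP table needs to change.

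The cost is one sentence in the protocol and some extra event forms over a 4-week follow-up.

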4.4 Study group blinding

Subjects, investigator staff, persons performing the assessments, and the clinical trial team will be blinded to assigned study group. Baseline laboratory values will not be blinded to the subjects, investigator staff, and the clinical team. Additional lipid labs will be prohibited for the 4 week participation period. The Day 28 labs will not be blinded.

It is expected that the need for unblinding of a patient's study group will be extremely rare. Every effort should be made to preserve the blind unless there is a compelling reason that knowledge of the specific treatment would alter the medical care of the patient.

5 Informed consent procedures

Eligible subjects may only be included in the study after providing IRB approved informed consent. Informed consent must be obtained before conducting any study-specific procedures. Subjects will be prescreened using historical laboratory values within 13 months of screening prior to consenting. Subjects that screen fail will not be eligible for rescreening.

6 Visit schedule and assessments

Subjects should be seen for all visits/assessments as outlined in the assessment schedule. The baseline and final visits will be completed in-person or remotely.

The fasting lipid draw and complete metabolic panel (CMP) at Day 0 and Day 28 must be obtained from a Cleveland Clinic lab. Recently acquired lipid labs and complete metabolic panel may be used in place of a Day 0 lab draw if acquired within 4 weeks of screening at a Cleveland Clinic lab and performed in the fasting state. Subjects are to remain on study medication/supplement until Day 28 labs are drawn.

Study personnel will use the following historical information to input into the ASCVD risk calculator to determine eligibility:

- Age
- Gender
- Race
- Systolic blood pressure
- Diastolic blood pressure
- Treatment for high blood pressure and diabetes
- Current smoking status

If a historical blood pressure is not found within 1 year of screening, patient reported is acceptable.

Lipid panel, hs-CRP will be collected at the initial visit and Day 28.

- Lipids: Indirect **LDL-C** (Total Cholesterol, HDL-C, and Triglycerides)
- Inflammatory markers: **hs-CRP**

Table 7-1 Assessment Schedule

Activity	Study Day	
	Day 0 ^b	Day 28 ^{b,f} +4/-4 days
Informed consent obtained ^b	X	
Demographics	X	
Medical history	X	
Eligibility confirmed & subject randomized ^h	X	
Body weight ^g	X	
Height ^g	X	
Concomitant Medication/supplements	X	X

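### Protocol 8.1.1 defines the only positive relatedness category by package-insert listing and the other two by causality, so some adverse events fit no category and others fit two

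*Protocol*

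**What the plan says.** Protocol 8.1.1, under Relatedness, opens with: "The relatedness of an adverse event to the study medication/supplement will be assessed by the Investigator for each submitted adverse event form". Three categories follow.

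- *Possibly Related* is worded in terms of listing: "An adverse event that is noted in the package insert".
- *Unknown*, by contrast, is worded in terms of cause: "An adverse event that cannot be determined to have a causal relationship with either the study medication/supplement or study procedure".
- *Not Related* is also a matter of cause, and covers events for which the investigator has ruled out a causal link to product and procedure alike.

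The same section makes events reportable when they might be attributed to a study product or to a study procedure, with lab draws as the example. SAP 9.1 lists the three relatedness labels as one field of the adverse event listings, without definitions, and lists expected/unexpected status as a separate field. Neither document gives a second positive category, a causal definition of Possibly Related, or an order in which the categories apply.

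On blinding, Protocol 4.4 states: "Subjects, investigator staff, persons performing the assessments, and the clinical trial team will be blinded to assigned study group".

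**The concern.** The three categories do not answer the same question. One asks whether the event is on a label; the other two ask whether a product or procedure caused it. A scheme that mixes two criteria can leave gaps and overlaps, and this one has both.

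The gap lies where the protocol itself expects trouble. Protocol 3.2 warns that over-the-counter supplements may contain undeclared ingredients, and Protocol 4.3.5 refers to a record of supplement tainting. The effects of an undeclared ingredient need not appear in any insert. An investigator who concludes that such an event was caused by the product has no category in which to record that conclusion.

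The listing test is also hard to apply. The text refers to a single insert, but there are eight study groups, and blinded staff cannot tell which product's insert applies to a given participant. Two assessors could code the same event differently because they consulted different inserts.

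At stake is whether the relatedness field in the safety listings records the investigator's causal judgement.

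**Working it through.** The plan gives no figure to reproduce, so the check is an enumeration. The inputs are the three definitions in Protocol 8.1.1, applied literally. Two label states (listed, unlisted) crossed with four causal judgements (caused by product, caused by procedure, undetermined, judged not causal) give 2 × 4 = 8 combinations.

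| Label state | Causal judgement | Categories met | Number |
|---|---|---|---|
| Listed | Caused by product | Possibly Related | 1 |
| Listed | Caused by procedure | Possibly Related | 1 |
| Listed | Undetermined | Possibly Related and Unknown | 2 |
| Listed | Not causal | Possibly Related and Not Related | 2 |
| Unlisted | Caused by product | none | 0 |
| Unlisted | Caused by procedure | none | 0 |
| Unlisted | Undetermined | Unknown | 1 |
| Unlisted | Not causal | Not Related | 1 |

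Totals: 4 combinations meet one category, 2 meet two and 2 meet none (4 + 2 + 2 = 8).

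Next, suppose the categories are applied in printed order, which the text does not say. All 4 listed combinations become Possibly Related, and the 2 unlisted combinations that are undetermined or not causal keep their single category. That gives 4 + 2 = 6 with one category, 0 with two and 2 with none. The overlap goes, but a listed event judged not causal is now coded Possibly Related, against the investigator's judgement. No ordering can close the gap, because an order only chooses between categories that are already met.

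Lab-draw events show the mismatch most clearly. The lead-in sentence limits the assessment to the medication or supplement, while the definitions of Unknown and Not Related also name the study procedure. An event caused by a lab draw can be coded positive only if its type happens to be on a label, which has nothing to do with its cause.

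These are unweighted logical cases and not frequencies.

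Lastly, what depends on the field:

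- The 24-hour rule in Protocol 8.1.1 ("Adverse events resulting in death or serious injury are to be reported to the sponsor within 24 hours of learning of the event") does not refer to the relatedness code.
- The by-group summaries in Protocol 10.6.1 and SAP 9.1 count events without splitting them by relatedness, and SAP 9.1 plans no formal tests.
- The primary LDL-C analysis does not use the field.
- The Medical Monitor reports in SAP 10 may include the SAP 9.1 listings, so missing or conflicting codes can reach that review.

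**The case against.** The strongest case against giving this weight is that the gap is narrow and the field is descriptive. A suspected but undetermined unlisted event fits Unknown, so the gap needs a blinded investigator to reach a positive causal judgement about an unlisted event. Section 8.1.1 already applies a causal threshold before an event is reportable, which makes a pure labelling test the harshest reading. Blinded staff could consult the inserts of all the products. The adverse event form and the Medical Monitor Charter are not among the documents and may contain coding guidance. All of this stands as a limit on the size of the problem. None of it supplies the missing causal definition, and recording a positively judged event as Unknown would misstate the judgement.

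A reader might infer something stronger: that an event could never be both related and unexpected, so that suspected unexpected serious adverse reactions would be missed. The documents do not support this. Neither document defines unexpected, and an event noted in an insert might still count as unexpected in severity or nature. Section 8.1.1 also makes the reporting of "All Suspected Unexpected Serious Adverse Reactions (SUSARS) related to Rosuvastatin or supplements" a separate duty and does not derive it from the coded relatedness field.

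**Conclusion.** The point holds and is minor. Followed as written, the definitions give no correct code in 2 of the 8 logical combinations and two conflicting codes in another 2. The effect is limited to the relatedness field in the SAP 9.1 listings and to the Medical Monitor reports that may include them. It would be wrong to infer that safety reporting as a whole or the efficacy result is compromised. How many events are affected cannot be stated.

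The conclusion rests on a literal reading of 8.1.1 and on there being no coding guidance in the two documents. It needs no assumption about what unexpected means.

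**What to change.** In Protocol 8.1.1, make the three categories the three possible answers to one question, judged blind and regardless of labelling: is there a reasonable possibility that a study medication/supplement or a study procedure caused the event?

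- *Possibly Related*: there is a reasonable possibility.
- *Not Related*: there is no reasonable possibility.
- *Unknown*: the information is insufficient to make that judgement.

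Under this wording, an event whose cause is not established but is reasonably possible goes to Possibly Related, so Unknown becomes narrower than it is now. Name study procedures in the lead-in sentence. Use the insert or label only as the reference for the separate expected/unexpected status field in SAP 9.1, and carry the definitions into SAP 9.1 and the adverse event form guidance.

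The expectedness check should not be moved into the SAP 10 review. That review begins 3 months after the first enrolment and repeats every 3 months, so it could not support the 24-hour reporting of suspected unexpected serious adverse reactions in 8.1.1.

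The cost is wording in one protocol subsection, matching definitions in the SAP, and form guidance. Causal judgements will vary more between assessors than a label look-up would, and events already coded would need blind recoding.
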